Note: When a patient does **not have plaque present**, but has **elevated velocities** throughout the ICA and the CCA (i.e., normal ICA/CCA ratio <2) the statement **"elevated velocities, no plaque seen. Likely normal study"** will be used in place of calling a category of stenosis.

Note: Although our criteria are based upon PSV and EDV, ICA/CCA ratios are included on our reports. These **criteria are added** for use in interpretation of cases in which **PSV may not accurately reflect the degree of stenosis** (e.g., tandem lesions in innominate or CCA, contralateral occlusion, and elevated velocities in all vessels due to underlying cardiac disorder). In general, an ICA/CCA ratio of > 4 is suggestive of a $> 70\%$ stenosis (NASCET criteria).

Note: In the setting of a contralateral ICA occlusion, there is potential for overestimation of stenosis due to compensatory flow. This should be noted in the interpretive report when appropriate (e.g., velocities in 80-99% category contralateral to occlusion).

II. Common carotid artery interpretation:

50-99% stenosis Velocity shift with doubling of PSV across an area of plaque

III. External carotid artery interpretation:

Elevated velocities, plaque noted PSV > 200 cm/sec with significant plaque visualized

IV. Subclavian artery interpretation:

50-99% stenosis Velocity shift with doubling of PSV across an area of plaque or PSV > 275 cm/sec in proximal subclavian artery with turbulent flow and plaque noted

If turbulent flow is present but no plaque is visualized, findings may suggest more proximal subclavian artery stenosis

REFERENCES

Cleveland Clinic internal validation studies of carotid ultrasound examinations and angiograms.

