This study will evaluate a new technology called the Carotid Stenotic Scan (CSS) developed by CVR Global, a medical device company. The CSS device uses principles of cardiovascular resonance to detect low frequency pressure fluctuations associated with

flow disturbances in areas of significant arterial narrowing. The CSS device consists of three non-emitting (passive) piezoelectric sensors contained in a cushioned gel pad, linked through a Y-shaped collar that positions one sensor over each carotid artery and one sensor on anterior central chest in the area of the heart (figure). These device pads lie on the skin surface and do not emit any energy into the body; they only gather data transmitted from within the body. The piezoelectric sensors in the device detect very low frequency pressure fluctuations generated by altered hemodynamics caused by narrowing

of the carotid artery. The CSS scan takes about 1-2 minutes to gather data for real-time analysis by the processor on the device cart.

Description: Prospective study of evaluable patients presenting to the Cleveland Clinic Non-Invasive Laboratory for a clinically indicated complete carotid duplex ultrasound examination. We aim to enroll 300 subjects. We will enroll at least 100 patients who have moderate stenosis of one ICA based on prior ultrasound studies and up to 25 patients with known carotid FMD. Subjects who enroll in the study will undergo evaluation by both carotid duplex ultrasound and the CSS device. Carotid duplex studies will be read by a registered physician in vascular interpretation, blinded to the CSS device result, and degree of ICA stenosis will be determined according to velocity criteria adopted by Cleveland Clinic Non-Invasive Vascular lab. Findings from CSS device will be analyzed and degree of ICA stenosis will be categorized.

Objectives:

1. To determine agreement of degree of internal carotid artery narrowing as measured by the CSS device versus carotid duplex ultrasound.
2. To determine the reproducibility measures of carotid artery narrowing as measured by the CSS device.
3. To compare the degree of carotid artery narrowing as measured by the CSS device versus any other imaging modality used to evaluate the internal carotid artery (CTA, MRA or catheter based angiography) (pilot analysis)

4. Exploratory data regarding CSS device output in the setting of carotid artery occlusions and fibromuscular dysplasia (FMD).

Study Subjects:

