The study population will consist of adult patients (≥ 18 years) presenting to the Cleveland Clinic Non-Invasive Vascular Laboratory for a scheduled carotid duplex ultrasound to evaluate for carotid artery disease or in follow-up of known ICA stenosis. By design, we will enroll at least 100 patients who are known to have at least moderate stenosis of one ICA (i.e., PSV ≥ 125 cm/sec based upon the findings of prior imaging studies. In addition, a subset of up to 25 patients enrolled will include those with previously documented fibromuscular dysplasia of at least one ICA. Potentially eligible patients will be approached in the area where the ultrasound testing will be done by a qualified member of the study team prior to the ultrasound examination to explain the study and obtain appropriate informed consent.

Inclusion Criteria:

- Outpatients age ≥ 18 years sent to the vascular laboratory for carotid duplex examination for initial carotid ultrasound study or for follow-up of known carotid disease.
- Enrolled patients will include at least 100 subjects with at least moderate known stenosis (50-69% or greater, PSV ≥ 125 cm/sec) or occlusion of one or both ICAs
- Up to 25 patients with **known** fibromuscular dysplasia (FMD) of the internal carotid arteries.

Exclusion criteria:

- Age < 18 years.
- Hospitalized inpatients.
- Inability to provide informed consent.
- Prior history of carotid endarterectomy or carotid artery stent.
- Prior neck surgery
- Known prosthetic heart valve, known critical aortic stenosis, or study indication “preop” open heart or aortic surgery.

Study Visit Procedures: The research study will be conducted on the same day of the clinical carotid duplex study but may be performed prior to or after the scheduled carotid ultrasound (and any other vascular) examination(s), depending upon the patient schedule. After informed consent is obtained, limited medical history will be obtained, and self-reported height and weight will be recorded. The patient will undergo the standard of care carotid duplex examination and the CSS study procedure. Each subject will have a unique identifier number assigned that will be used on all ensuing study documents.

Medical History:

Data will be obtained by limited subject questionnaire and review of the electronic medical record, to include:

- Age on date of the study
- Sex
- Race, ethnicity
- Height and weight (self-reported)

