- Study indication (first carotid duplex in lab, surveillance of known carotid artery stenosis, fibromuscular dysplasia, other)
- Treated medical conditions, including:
- Coronary artery disease (History of myocardial infarction, angina + abnormal stress test, or prior coronary artery bypass grafting or stenting/PCI)
- History of congestive heart failure
- Left ventricular ejection fraction (if known and date of echocardiogram within the past 1 year)
- Known peripheral artery disease (PAD)
- History of transient ischemic attack
- History of stroke
- Did patient have TIA, stroke or symptoms of retinal ischemia within 30 days of ultrasound study
- Hypertension requiring medication therapy
- Hyperlipidemia requiring medication therapy
- Diabetes requiring medication therapy or diet
- History of smoking cigarettes (> 100 in lifetime)
- Known diagnosis of fibromuscular dysplasia
- Known history of internal carotid artery dissection
- History of COPD
- Any correlative imaging studies (CTA, MRA, angiography) within 1 month prior to the day of the carotid duplex examination

Follow-up and Correlative Examinations:

Within 3 months (+/- 7 days) following the date of the study visit, the electronic medical record will be queried for any interval correlative imaging studies (CTA, MRA, or angiography) and reports performed up to 1 month prior and 3 months after the duplex examination date. Report of findings will be document (i.e., % ICA stenosis by CTA/MRA).

Study Procedures (Appendix B)**Standard Clinical Procedures:**

The subject will undergo the clinically ordered clinical carotid duplex ultrasound as part of standard of care. Studies are performed using a standardized scanning protocol (Appendix C) by a Registered Vascular Technologist and interpreted by a Registered

Physician in Vascular Interpretation or otherwise qualified member of the medical staff. The vascular technologist and interpreting physician will be blinded to the output of the CSS study device.

- For purposes of this study, degree of ICA stenosis will be reported according to SRU consensus velocity criteria., Primary SRUCC parameter to determine % ICA stenosis will be peak systolic velocity, unless there is a clear indication for the use of a secondary parameter (ICA/CCA ratio, EDV), such as contralateral occlusion, tandem lesions, discrepancy between visual assessment of the plaque and PSV and others(4).

SRU Consensus Criteria (4)

| Primary Parameters | | Secondary Parameters | | |

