|-----------------------------------|----------------------------|------------------------------|-------------------|------------------|
| Degree of stenosis (%) | ICA PSV (cm/sec) | Plaque Estimate (%)* | ICA/CCA PSV Ratio | ICA EDV (cm/sec) |
| Normal | < 125 | None | <2.0 | <40 |
| < 50 | < 125 | <50 | <2.0 | <40 |
| 50-69 | 125-230 | ≥50 | 2.0-4.0 | 40-100 |
| ≥ 70 but less than near occlusion | >230 | ≥50 | >4.0 | >100 |
| Near occlusion | High, low, or undetectable | Visible | Variable | Variable |
| Total occlusion | Undetectable | Visible, no detectable lumen | Not applicable | Not applicable |

*Plaque estimate (diameter reduction) with gray-scale and color Doppler US.

- Degree of stenosis per the Cleveland Clinic Non-invasive Vascular Laboratory will also be recorded (ECST based):
 - 0-19% stenosis PSV < 105 cm/sec no plaque
 - 20-39% stenosis PSV < 105 cm/sec plaque visualized
 - 40-59% stenosis PSV 105 – 150 cm/sec
 - 60-79% stenosis PSV > 150 cm/sec but EDV ≤ 135 cm/sec
 - 80-99% stenosis PSV > 240 cm/sec and EDV > 135 cm/sec
 - Occlusion – absent flow on extensive Doppler interrogation
 - Ultrasound features of carotid FMD (increased velocity and turbulent flow mid to distal ICA).

The following ultrasound parameters will be recorded for each side:

- Distal CCA peak systolic velocity
- Highest origin/proximal to mid ICA peak systolic velocity (PSV)
- Associated end diastolic velocity (EDV) for highest PSV
- ICA/CCA PSV Ratio
- Presence of plaque in the ICA (defined as wall thickness ≥ 1.5 mm)
- Presence of distal ICA waveform dampening (qualitative)

- Presence of post-stenotic spectral and/or color Doppler turbulence
- SRU Consensus Criteria % ICA Stenosis
- Cleveland Clinic Criteria % ICA Stenosis

For FMD subset: highest ICA mid/distal PSV and associated EDV

CSS Study Procedures:

Subjects will have a noninvasive CSS assessment as described below before or after the carotid duplex ultrasound. It is expected that the entire CSS evaluation will take approximately ten minutes. See Appendix A for the CSS Study Procedure.

Study Data Collection

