Each subject will have a hard copy file with case report information and source documents, medical history questionnaire, CSS output, and the ultrasound reports. These individual files will be maintained with identifiers, including the signed consent form, and maintained in a locked filing cabinet accessible to the study coordinator and the authorized investigators. A Redcap database will be developed and maintained for clinical data entry and this will be housed on a password-protected network. All data that the sponsor receives will either be aggregate data or de-identified case report files. Deidentified ultrasound images and de-identified correlation study images and report may be requested by the sponsor for cases in which CSS results and duplex findings were discrepant.

Statistical Analysis Plan and Power Calculation: Primary analysis % agreement CSS and carotid duplex ultrasound (SRUCC interpretation) for ICA stenosis. Agreement will be assessed using the intraclass kappa coefficient (and corresponding 95% confidence intervals) for categorical data. Percent stenosis from both the CSS measurement and the duplex ultrasound will be categorized as follows:

| Carotid Duplex by SRU Consensus | Simplified Duplex Category by SRU Consensus | CSS Device |
|---------------------------------|---|------------------|
| Normal | <50% | <50% |
| <50% | <50% | <50% |
| 50-69% | 50-69% | 50-69% |
| ≥70% | ≥70% | ≥70% |
| Occlusion | Occlusion | Exploratory data |
| U/S Features of FMD | FMD | Exploratory data |

It is anticipated that approximately 40% of total patients will have an ICA stenosis of 50% or greater. A sample of at least 300 patients (up to 500 carotid arteries) will have 90% power to detect an intraclass correlation coefficient of 0.80, assuming a null hypothesis of 0.65, with a 2-sided alpha of 0.05.

The secondary endpoint of reproducibility of the CSS measurement will be analyzed using the continuous stenosis measurement. Each CSS measurement will be repeated and the Intraclass Correlation Coefficient (ICC) will be calculated. The ICC is an index of the reliability of measurements from the same operator. Pearson and/or Spearman correlation coefficients and plots may also be produced.

Separate exploratory analyses will address the following:

- 1) Correlation of CSS results to duplex ultrasound results in those with ICA by duplex occlusion

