APPENDIX B: CSS STUDY VISIT CHECKLIST

Inclusion (all must be answered “YES”/checked off):

- Patient at least 18 years old
- Seen as an outpatient
- Scheduled for a carotid duplex ultrasound examination for initial or follow-up evaluation of known carotid disease
- Able to give informed consent in English

Patient known to qualify for subgroup?:

- At least moderate stenosis (PSV > 125 cm/sec) or occlusion of one or both ICAs on a prior CCF duplex study
- Known fibromuscular dysplasia of one or both ICAs

Exclusion criteria checked (confirm none of the following are true):

- Prior history of carotid endarterectomy or carotid artery stent
- Prior history of prosthetic heart valve
- Known critical severe aortic stenosis (AVA < 1 cm/sec)
- Indication for carotid duplex ultrasound is “pre-op” for open heart surgery or aortic surgery
- Prior neck surgery

Study Procedures:

- Informed consent complete and copy given to patient
- Generate subject ID number
- Medical history form, height and weight
- Carotid duplex ultrasound study completed (can be done before or after consent or CSS exam)
- 5 minute rest period
- 1st CSS measurement
- 2nd CSS measurement
- Validate parking
- Code database form

Research Coordinator/ Investigator Signature

Date

APPENDIX C: Cleveland Clinic Non-Invasive Laboratory Carotid Duplex Examination Protocol (Native Carotid Arteries)

EXTRACRANIAL CAROTID DUPLEX ULTRASOUND

I. PURPOSE

Duplex scanning permits accurate localization of disease in the extracranial carotid and vertebral arteries. Spectral analysis of velocity waveform permits accurate classification of disease in the internal carotid artery into categories based on the extent of diameter reduction.

II. INDICATIONS

- A. Transient ischemic attack (TIA)
- B. Asymptomatic cervical bruit
- C. Stroke/cerebrovascular accident (CVA)
- D. Suspected subclavian steal
- E. Screening of patients prior to cardiac or vascular surgery with asymptomatic bruit or high risk for carotid artery stenosis
- F. Post carotid intervention patients (endarterectomy, stent, etc.)
- G. Pulsatile mass in either the carotid or subclavian region
- H. Follow up studies on patients with known carotid disease
- I. Suspected carotid artery dissection

III. LIMITATIONS

- A. Recent neck surgery (i.e., endarterectomy)
- B. Patients who are unable to lie flat or still may prove difficult to scan

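### Blinding is stated in one direction only: CSS may follow the same-day duplex, and nothing keeps those who acquire and record CSS from knowing the duplex result

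*Protocol*

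**What the plan says.** **Blinding of duplex to CSS** is stated twice. The Description has "Carotid duplex studies will be read by a registered physician in vascular interpretation, blinded to the CSS device result", and Standard Clinical Procedures has "The vascular technologist and interpreting physician will be blinded to the output of the CSS study device".

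**Order of the tests** is left open in three places. Under Study Visit Procedures the research study is done on the day of the duplex and "may be performed prior to or after the scheduled carotid ultrasound". CSS Study Procedures has "Subjects will have a noninvasive CSS assessment as described below before or after the carotid duplex ultrasound". Appendix B lists "Carotid duplex ultrasound study completed (can be done before or after consent or CSS exam".

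**Acquiring and recording CSS.** The introduction describes one Y-shaped collar with a sensor over each carotid and one on the chest, and "real-time analysis by the processor on the device cart". In Appendix A an operator places the collar by hand, starts the scan once the device has verified the signal, stops it after 30 seconds, and then repeats the sequence once. The Description says in the passive voice that CSS findings will be analysed and categorised, and names nobody. The statistical section adds "Percent stenosis from both the CSS measurement and the duplex ultrasound will be categorized as follows" and prints the cut-offs. Study Data Collection puts the CSS output and the ultrasound reports in one subject file.

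**Consent.** Study Subjects has patients approached "by a qualified member of the study team prior to the ultrasound examination to explain the study and obtain appropriate informed consent".

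**The concern.** The study asks whether CSS, read on its own, puts an artery in the same stenosis category as duplex. That requires each test to be done without knowledge of the other. Here only the reference test is protected. If the person running CSS already knows that duplex found a narrowed or a normal artery, that knowledge can affect how carefully the sensors are positioned, whether a recording counts as valid, and whether a scan is quietly redone. Each of these would tend to pull CSS towards duplex and so flatter the primary result.

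Test order and blinding are rules of conduct that the protocol sets for itself. If the CSS recordings are made with the duplex result known, no later analysis plan can restore their independence.

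**Working it through.** No arithmetic decides this point. The protocol's power statement (null 0.65, target 0.80, 90% power) neither depends on it nor helps to size it. The check is a reading of every section that deals with blinding, test order, CSS operation and data handling.

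**1. Who is blinded to what?**

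| Person | Blinded to the other test? | Where |
|---|---|---|
| Duplex technologist | Yes | Standard Clinical Procedures |
| Duplex reader | Yes | Description; Standard Clinical Procedures |
| CSS operator | Not stated | Appendix A is silent |
| Person categorising CSS | Not stated, no role named | Description |
| Person entering the CSS result | Not stated | Study Data Collection; Appendix B |

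**2. Can the duplex come first?** Yes, in all three places that address order. Appendix B, as printed, puts duplex completion above a rest period and the two CSS measurements, then the database form, over a single signature line for a coordinator or investigator. One person could therefore have access to the duplex finding while doing CSS. The protocol does not say that this happens, but nothing prevents it.

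**3. Which CSS steps could that knowledge influence?**

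- Computing the result: protected, since the cart processor does it.
- Signal quality: largely protected. The operator checks the display and the device verifies the signal.
- Recording length and number of scans: fixed at 30 seconds and two scans.
- Left versus right: one scan records both carotids, so a repeat redraws both sides together.
- Categorisation: limited by the printed cut-offs, although no blinded role is assigned.
- Data entry: checkable against the CSS output in the source file.
- Sensor placement: not protected. It is done by hand to a described site.
- Judging a recording uninterrupted: not protected. The word is a criterion, but a person applies it.
- Repeats: two scans are prescribed, but the protocol does not require a stopped or redone scan to be logged.

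The last three are the open routes.

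**4. Does same-day blinding cover all prior knowledge?** No. At least 100 of the planned 300 subjects (100/300, one third) are enrolled with known moderate or worse stenosis or occlusion. The Appendix B checklist records that status above the CSS measurements. An operator who never sees the same-day duplex may still know that a patient has disease.

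**5. Consent timing.** Study Subjects places approach and consent before the ultrasound, whereas Appendix B lets the duplex precede consent. The two do not agree. This is a separate, minor wording conflict, and no direction of effect follows from it.

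**The case against.** The strongest reply is that CSS is an automatic test. The processor produces the number, the device checks the signal, the duration and the number of scans are prescribed, and the output is retained, so there is little for an operator's knowledge to act on. The checklist item is a completion tick with no field for that day's duplex result. The physician's reading may not exist when CSS is run. The technologist and reader could not run CSS and watch its display before finishing their own part without breaking their blinding. Most of this stands, and it is why the route is called narrow. It does not close the route: automatic processing does not control which signal is acquired or kept, and no section withholds scan findings from the CSS operator.

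A reader might infer more than the document supports:

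- **That an operator could rerun a narrowed side and accept a normal one.** The collar records both sides in a single scan, so the sides of one patient cannot be accepted or rejected separately.
- **That repeats are at the operator's discretion.** Appendix A prescribes two scans. Further scans driven by the result would depart from it. The gap is only that none need be logged.
- **That kappa would rise by some stated amount.** Any such figure merely restates an assumed share of disagreements turned into agreements, and the protocol gives no basis for one.
- **That the operator does know the duplex result.** The text permits this but does not say it.

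**Conclusion.** The point holds in a limited form. Blinding runs one way, CSS may follow duplex on the same day, and no section keeps those who acquire, accept, categorise or enter CSS from knowing the duplex result. That leaves the primary agreement measure open to an avoidable bias, which would probably be upward. Its size is unknown and cannot be derived from the document. It depends on how often CSS follows duplex, how often the operator learns the finding, and how much placement and acceptance respond to it; none of these is given. The safeguards listed above make a large effect less plausible but do not exclude an effect. The gap is worth closing because prevention is cheap and later repair is not possible. It is not evidence that the results would be invalid.

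**What to change.** In CSS Study Procedures and Appendix B:

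1. State that those who acquire, accept, categorise and enter CSS do not know the same-day duplex result.
2. Do CSS first where the schedule allows. Otherwise record the CSS output before any duplex finding is disclosed to the CSS operator.
3. Log every stopped or redone scan, with the reason.
4. Where feasible, have the prior-stenosis item on the checklist completed by someone else or after the CSS scans. Acknowledge that knowledge of prior stenosis in the enriched subgroup may not be fully removable.

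Separately, as a minor correction, reconcile Study Subjects with Appendix B on whether the duplex may precede consent. Which of the two scans feeds the primary analysis may be left to the SAP.

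Cost: a few sentences and slightly less scheduling flexibility. No patient procedure is added. Steps 1 to 3 need no extra staff, and step 4 needs none if the item is completed after the scans.
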